ANNEX 3. MANAGE SITE AND PHYSICIAN / INVESTIGATOR SELECTION, CONTRACTING, AND TRAINING

Sites may be identified several ways:

- Suggestions from internal colleagues. For instance, obtaining suggestions from local affiliates is crucial.
- Suggestions from external stakeholders, such as vendor if study is outsourced or key external experts
- Existing data such as externally accessed prescriber data, participating physician databases, commercial listings and / or EMR, national registries, marketing information or other secondary data sources.

A comprehensive site list, including contact information for the sites, should be developed well ahead of protocol finalization and the site selection strategy should be clearly outlined in the protocol and operational documents.

Conduct site feasibility questionnaire, if applicable

To ensure that the most appropriate sites will participate in the study, a Site Feasibility Questionnaire (SFQ) can be useful in order to ask sites about their interest and ability to conduct the study. This is especially the case if many sites need to be identified.

Sites may find it helpful to have the study summary so they have a background regarding the study. Depending on local requirements, some countries may require a phone call prior to any study documents being sent.

Obtain signed confidentiality agreement (CDA) first

Before sharing information with a site, a confidentiality agreement (CDA) with the site should be signed. Signatures may take time, so, this should be considered in the study timelines.

Considerations when selecting a site:

Below are some criteria for selecting a site:

- **Ability to conduct the study:** Most importantly, the site should be able to conduct the study as outlined in the study summary or protocol.
- **Representativeness:** Sites should not only be restricted to only those with previous research experience but optimized to ensure broad representation of the sites that typically diagnosis and / or treat the indication of interest in a given country. This is to ensure the study provides a representative picture of the real-world practice setting. Thus, the team should evaluate criteria such as the representativeness of practice type, practice size, and professional qualifications. Local input is often crucial.
- **Enrolment rate:** It is important to ask the site how many patients they can enrol. The team should evaluate if this aligns with the requirements of the study summary or protocol. When considering number of patients per site, it is advisable to consider if site enrollment caps are needed to be instituted to avoid the potential for center effects which drive results.
- **Resources:** It is important to confirm that the site has the needed resources (staff, computer equipment, etc) to conduct the study. Moreover, sites may have a heavy

workload or may prioritize other studies, especially if they are conducting clinical trials at the same time.

- **Compliance:** A due-diligence review should be conducted to ensure there are no compliance issues with investigators.

Number of sites:

- The number of sites depends on several factors. Based on sample size needed, it is important to determine the how many patients can be enrolled per site within the timeline of the study. Having several sites will help avoid individual sites dominating the results and potentially compromising the representativeness. Moreover, the team should consider identifying more sites than needed, including “back-up sites” in case site(s) drop out or more sites are needed in case, enrolment rates are lower than expected.

Verification from stakeholders and OPU’s

- The study team should review the results of the SFQ, if done, to determine which sites may be selected for site qualification visits (QV) or phone calls (or “pre-study contact”).
- The list should be verified with each OPU in terms of the target physician specialties and site types that reflect standard of care for the indication under study (e.g. If patients are followed most often by cardiologists in a tertiary care / academic setting, this should be built into the final site breakdown for an OPU). Clear communication pathways should be discussed and agreed upon to ensure that sites are receiving consistent information not only during start-up, but throughout the study.
- The site list should also be reviewed by the local teams to determine if there are existing relationships with the site staff, or if similar studies in the same indication have been previously managed by the team.

Conduct qualification call:

- During the qualification call, the study staff should discuss the protocol (or study summary), patient population of interest, and reconfirm the site’s ability to conduct the study.
- Sites should be informed of the budget expectations, and relevant Boehringer Ingelheim or vendor specific business processes that may impact the site
- The results of the site qualification calls / visits are reported to the study team, after that the final selection of the sites for the study can take place.

ANNEX 4. PHYSICIAN'S GLOBAL ASSESSMENT FOR GENERALIZED PUSTULAR PSORIASIS (GPPGA)

Erythema

- 0 = Clear: Normal or postinflammatory hyperpigmentation
- 1 = Almost Clear: Faint, diffuse pink or slight red
- 2 = Mild: Light red
- 3 = Moderate: Bright red
- 4 = Severe: Deep fiery red

Pustules

- 0 = Clear: No visible pustules
- 1 = Almost Clear: Low density occasional small discrete (non coalescent) pustules
- 2 = Mild: Moderate density grouped discrete small pustules (non coalescent)
- 3 = Moderate: High density pustules with some coalescence
- 4 = Severe: Very high density pustules with pustular lakes

Scaling/crusting

- 0 = Clear: No scaling and no crusting
- 1 = Almost Clear: Superficial focal scaling or crusting restricted to periphery of lesions
- 2 = Mild: Predominantly fine scaling or crusting
- 3 = Moderate: Moderate scaling or crusting covering most or all of lesions
- 4 = Severe: Severe scaling or crusting covering most or all lesions

PGA Score for GPP

- 0 = If mean=0 for all three components
- 1 = If $0 < \text{mean} < 1.5$
- 2 = If $1.5 \leq \text{mean} < 2.5$
- 3 = If $2.5 \leq \text{mean} < 3.5$
- 4 = If $\text{mean} \geq 3.5$

**ANNEX 5. PSORIASIS AREA AND SEVERITY INDEX FOR
GENERALIZED PUSTULAR PSORIASIS (GPPASI)****Severity****Erythema**Head 0=Clear 1=Almost clear 2=Mild 3=Moderate 4=SevereTrunk 0=Clear 1=Almost clear 2=Mild 3=Moderate 4=SevereUpper Limb 0=Clear 1=Almost clear 2=Mild 3=Moderate 4=SevereLower Limb 0=Clear 1=Almost clear 2=Mild 3=Moderate 4=Severe**Pustules**Head 0=Clear 1=Almost clear 2=Mild 3=Moderate 4=SevereTrunk 0=Clear 1=Almost clear 2=Mild 3=Moderate 4=SevereUpper Limb 0=Clear 1=Almost clear 2=Mild 3=Moderate 4=SevereLower Limb 0=Clear 1=Almost clear 2=Mild 3=Moderate 4=Severe**Scaling**Head 0=Clear 1=Almost clear 2=Mild 3=Moderate 4=SevereTrunk 0=Clear 1=Almost clear 2=Mild 3=Moderate 4=SevereUpper Limb 0=Clear 1=Almost clear 2=Mild 3=Moderate 4=SevereLower Limb 0=Clear 1=Almost clear 2=Mild 3=Moderate 4=Severe**AREA OF INVOLVEMENT**

Provide the percentage of involved area in each body region (=area affected by pustules scaling [not the area for each component separately])

Head 0=0% 1=1 to < 10% 2=10 to < 30% 3=30 to < 50% 4=50 to < 70% 5=70 to < 90% 6=90 to 100%

Trunk 0=0% 1=1 to < 10% 2=10 to < 30% 3=30 to < 50%

4=50 to < 70% 5=70 to < 90% 6=90 to 100%

Upper Limb 0=0% 1=1 to < 10% 2=10 to < 30% 3=30 to < 50%

4=50 to < 70% 5=70 to < 90% 6=90 to 100%

Lower Limb 0=0% 1=1 to < 10% 2=10 to < 30% 3=30 to < 50%

4=50 to < 70% 5=70 to < 90% 6=90 to 100%

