9.3.2.3 Further outcomes

The further outcomes are as follows:

- A GPPASI 75 at Week 4 (if collected)
- A GPPASI 50 at Week 1 (if collected)
- A GPPASI 50 at Week 4 (if collected)
- The percent reduction in GPPASI from baseline at Week 1 (if collected)
- The percent reduction in GPPASI from baseline at Week 4 (if collected)
- Change from baseline in pain VAS score at Week 4 (if collected)
- Change from baseline in PSS score at Week 4 (if collected)
- Investigator's overall effectiveness assessment at Week 1 and/or Week 4

The GPPASI is provided in [Annex 5](#). It is an adaptation for GPP patients of the Psoriasis Area and Severity Index (PASI), an established measure of severity and area of psoriatic lesions in patients with psoriasis [[R96-3541](#)]. Similar adaptations have been used for palmo-plantar psoriasis (PPP) [[R16-3360](#)]. In the GPPASI, the induration component was substituted with the pustules' component. It is a tool that provides a numeric scoring for a patient's overall GPP disease state, ranging from 0 to 72. It is a linear combination of percent of surface area of skin that is affected by erythema, pustules and scaling and the severity of erythema, pustules, and scaling (desquamation) over 4 body regions.

The pain VAS instrument is provided in [Annex 6](#). The pain VAS is a unidimensional measure of pain intensity [[R18-1989](#)]. The respondent is asked to place a vertical (|) mark on the horizontal line to indicate the severity of the pain. Using a ruler, the score is determined by measuring the distance (mm) on the 10-cm line between the "no pain" anchor and the

patient's mark, providing a range of scores from 0–100. A higher score indicates greater pain intensity.

The PSS instrument is provided in [Annex 7](#). The PSS is a 4-item patient-reported outcome (PRO) instrument that was developed to assess the severity of psoriasis symptoms in patients with moderate to severe psoriasis [[R18-1990](#)]. The symptoms included are pain, redness, itching, and burning. Current symptom severity is assessed using a 5-point scale ranging from 0 (none) to 4 (very severe). The symptom scores are added to an unweighted total score (range: 0 to 16).

The overall effectiveness assessment is performed at the investigator's discretion. The information includes:

- Improved: If determined as there is any effect of maintaining or improving symptoms.

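### As printed, Annex 5 leaves erythema out of the GPPASI area while section 9.3.2.3 includes it; in patients left with redness alone this can overstate percent reduction and sometimes flip GPPASI 75

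*Protocol*

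**What the plan says.** Section 9.3.2.3 of the protocol introduces the GPPASI as an adaptation of the PASI: "In the GPPASI, the induration component was substituted with the pustules' component". Erythema therefore remains one of its three components. The section describes the index in these words: "It is a linear combination of percent of surface area of skin that is affected by erythema, pustules and scaling", together with the severity of the same three signs over four body regions, "ranging from 0 to 72". It refers the reader to Annex 5 for the instrument.

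Annex 5 asks for a severity score of 0 to 4 for erythema, pustules and scaling in each of the head, trunk, upper limb and lower limb. It then asks for one area score per region, coded 0 to 6, with this instruction: "Provide the percentage of involved area in each body region (=area affected by pustules scaling [not the area for each component separately". Erythema is not mentioned there.

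The outcomes that use the index are all listed under further outcomes: GPPASI 75 at Week 4 ("A GPPASI 75 at Week 4 (if collected"), GPPASI 50 at Weeks 1 and 4, and percent reduction at Weeks 1 and 4. Each applies only where the GPPASI is collected.

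**The concern.** The rater works from the annex. Read as printed, it asks for the erythema grade in a region but not for the skin that is only red. Section 9.3.2.3 counts that skin. Two sites that follow different parts of the same protocol could give one patient different scores.

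The difference is largest in a patient whose pustules and scale have gone but whose redness remains. If area multiplies severity, as in the usual PASI, an area score of 0 cancels whatever erythema grade was recorded, and partial improvement is reported as complete clearance.

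The GPPGA would not reveal this. It uses no area, and in Annex 4 a patient with erythema 4, pustules 0 and scaling 0 has a mean of 4/3 = 1.33, which is a GPPGA score of 1 and so counts as a response. The GPPASI is the listed physician scale that scores extent. With a target of 21 patients, one reclassified patient moves a response rate by 1/21 = 4.8 percentage points, or by more if the GPPASI is collected in fewer.

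**Working it through.** **Inputs.** From Annex 5: severities E (erythema), P (pustules) and S (scaling), each 0 to 4, and one area score A, 0 to 6, per region. From section 9.3.2.3: range 0 to 72. Not in the protocol: the combining formula and region weights. I assume the usual PASI form, the sum over regions of w × (E + P + S) × A, with weights summing to 1. The patient scores below are illustrative and equal in all four regions, so the index reduces to (E + P + S) × A.

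**Step 1: the stated range.** The product form gives a maximum of (4 + 4 + 4) × 6 = 72, which agrees with section 9.3.2.3. An unweighted sum over four regions, 4 × (4 + 4 + 4 + 6), also gives 72. The range fits the product form but does not prove it.

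**Step 2: redness alone at Week 4.** Baseline E = 3, P = 3, S = 2, A = 4: 8 × 4 = 32. At Week 4, E = 3 over the same skin, P = S = 0.
- Area including erythema: 3 × 4 = 12. Reduction 1 − 12/32 = 62.5%. GPPASI 50 met, GPPASI 75 missed.
- Area as printed in Annex 5: 3 × 0 = 0. Reduction 100%. Both met.

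**Step 3: when GPPASI 75 flips.** With P = S = 0 at follow-up, remaining erythema e and erythema area a, the erythema-inclusive reduction is 1 − (e × a) / [(E + P + S) × A]. For baseline 3/3/3 and A = 5 the baseline score is 45. The annex reading gives 100% in every row.

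| e | a | Score | Reduction with erythema in area | GPPASI 75 |
|---|---|---|---|---|
| 3 | 5 | 15 | 66.7% | missed |
| 3 | 4 | 12 | 73.3% | missed |
| 3 | 3 | 9 | 80.0% | met |
| 2 | 5 | 10 | 77.8% | met |
| 1 | 5 | 5 | 88.9% | met |

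The classification changes only while redness stays near its baseline grade and extent. Over 1,458 score combinations (baseline severities 2 to 4, baseline area 3 to 6, pustules and scale cleared, erythema present but no worse than baseline), the inclusive score misses GPPASI 75 in 188 (12.9%) and GPPASI 50 in none. These count score combinations, not patients.

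**Step 4: GPPASI 50.** If erythema neither worsens nor spreads, the inclusive reduction is at least (P + S) / (E + P + S), using baseline scores. That is below 50% only if baseline E exceeds P + S. With baseline P and S both 2 or more this cannot occur, since E is at most 4.

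**Step 5: the opposite direction.** Baseline 3/3/3, with erythema over area score 6 and pustules or scale over area score 3. Follow-up 2/1/1, with both areas at 3.
- Area including erythema: 9 × 6 = 54 to 4 × 3 = 12. Reduction 77.8%, GPPASI 75 met.
- Area as printed: 9 × 3 = 27 to 12. Reduction 55.6%, GPPASI 75 missed.

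Here the annex wording understates response.

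**Step 6: if the formula were the plain sum.** The Step 2 patient has baseline 4 × (8 + 4) = 48. As printed, follow-up is 4 × (3 + 0) = 12, a 75% reduction. With erythema in the area it is 4 × (3 + 4) = 28, a 41.7% reduction. The index does not fall to 0, but the two definitions still classify the patient differently, here on GPPASI 50 as well.

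**The case against.** The strongest objection is that the annex phrase is broken. It sets two nouns side by side with no connector, so a word or symbol may have been lost in the source or when the PDF was read. Its bracket asks for one joint area across the components, and the components listed just above it include erythema. The intended rule may well be that of section 9.3.2.3. This stands: the original must be checked, and if erythema is named there the conflict disappears.

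Stronger readings are tempting, and the documents do not support them:
- A reader might infer that GPPASI 50 and GPPASI 75 are overstated in general. Under the product form GPPASI 50 is met either way in the worked example, GPPASI 75 flips only in a narrow band, and Step 5 shows the bias reversing.
- A reader might take the fall to 0 as fact. It depends on a product formula the protocol does not state. The absence of a formula is not itself raised here, since it may be in the statistical analysis plan.
- A reader might assume that redness without pustules or scale is the expected state at Weeks 1 and 4. The protocol gives no frequency for it.
- A reader might see a gap in the area codes, which run "0=0% 1=1 to < 10% 2=10 to < 30% 3=30 to < 50". If percentages are recorded as whole numbers there is no gap, and no consequence has been shown, so it is not part of this point.

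Materiality is also fairly challenged. Safety is primary, the mandatory effectiveness measures are the GPPGA and its pustulation sub-score, and all analyses are described as exploratory.

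**Conclusion.** The point holds as a wording conflict on a scoring form: as printed, Annex 5 and section 9.3.2.3 define the GPPASI area differently. Under the product form, percent reduction is overstated in a patient left with redness alone, by 37.5 percentage points in the worked example (100% against 62.5%). GPPASI 75 can flip when that redness stays near baseline. No general direction of bias follows once pustules or scale persist. The limited effect on GPPASI 50 is also a product-form result. These sizes rest on the assumed formula, illustrative scores and the printed annex phrase being complete. Severity is low, because only exploratory, if-collected further outcomes are touched. It is still worth correcting, because the annex is the instruction raters follow.

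**What to change.** Check the Annex 5 area instruction in the original document. If erythema is absent there too, reword it to *area affected by erythema, pustules and/or scaling*, keeping the note that one joint area is wanted per region, and put the same words in the eCRF. If the original already names erythema, only the eCRF text needs confirming.

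The cost is one line in the annex and one in the eCRF. Section 10.1 requires amendments to be approved before they are implemented, so the change is best bundled with the next amendment. If any GPPASI has already been scored, ask those sites which area they used. Response in patients left with redness alone may look less favourable than under the printed annex wording.

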ANNEX 6. PATIENT'S ASSESSMENT OF PAIN VISUAL ANALOG SCALE (VAS)

How much pain have you had because of your generalized pustular psoriasis (GPP) in the past week?

Place a vertical (|) mark on the line to indicate the severity of the pain.

No pain

Severe pain

0 ————— 100

ANNEX 7. PSORIASIS SYMPTOM SCALE (PSS)

Listed below are a set of problems that people with psoriasis have said are important. For each question, click on the circle that best describes the severity of your symptoms during the past 24 hours. Please answer every question.

1. How severe was your pain from your psoriasis during the past 24 hours?

- None
- Mild
- Moderate
- Severe
- Very severe

2. How severe was the redness from your psoriasis during the past 24 hours?

- None
- Mild
- Moderate
- Severe
- Very severe

[figure not shown]
3. How severe was your itching from your psoriasis during the past 24 hours?

- None
- Mild
- Moderate
- Severe
- Very severe

4. How severe was your burning from your psoriasis during the past 24 hours?

- None
- Mild
- Moderate
- Severe
- Very severe

ANNEX 8. OBSERVATIONAL AND NON-INTERVENTIONAL STUDY (ONIS) ADVERSE EVENT FORM

	Observational and Non-Interventional Study (ONIS) Adverse Event Form	BI Study No:	Country:
		Site No:	Subject No:

No. of pages, including this page:

[figure not shown]
To: Boehringer Ingelheim [or CRO] [Address] [Fax number]	From: [site stamp]
--	-----------------------

BY SIGNING THIS FORM, YOU ARE CONFIRMING THAT THE INFORMATION CONTAINED HEREIN IS ACCURATE.

Record all dates in ddmmmyyyy format (e.g. 01Jan2016)

Type of report	Date	Investigator's signature	Remarks
 Initial		_____	
 Follow-up		_____	
 Follow-up		_____	
 Follow-up		_____	
 Follow-up		_____	
 Follow-up		_____	
 Follow-up		_____	

SUBJECT DEMOGRAPHICS		
Year of birth:	Height __(cm) If unknown, record 'UNK'	Weight __(kg)
Sex:  Male  Female	Pregnant:  No  Yes	_____ weeks
If pregnant, please submit completed Pregnancy Monitoring Form for Studies		

	Observational and Non-Interventional Study (ONIS) Adverse Event Form	BI Study No:	Country:
		Site No:	Subject No:

EVENT INFORMATION

Record all dates in ddmm/yyyy format (e.g. 01Jan2016). If ongoing, enter 'CONT.' Record all times in 24-hour (hh:mm) format. If time is unknown, record 'UNK.'

	Event No. []			
Adverse Event term (If available, enter the diagnosis)				
Onset date				
Onset time				
End date				
End time				
Was the event serious?	 Yes  No			
If serious, please mark reason for seriousness	Results in death			
	Immediately life-threatening			
	Persistent or significant disability / incapacity			
	Requires / prolongs hospitalisation			
	Congenital anomaly/birth defect			
Other comparable medical criteria (specify in Description of Event section)				
Was the event a protocol-specified Adverse Event of Special Interest (AESI)?	 Yes  No			
Is there a reasonable causal relationship between the Adverse Event and: (provide description of rationale, other possible causes on page 3)				
BI studied medication or BI product given for the disease in scope of ONIS	 Yes  No			
Concomitant medications: Please refer to concomitant medication section to document causal relationship.				
Outcome of event (check only one)				
Recovered (report AE end date above)				
Not yet recovered				
Recovered with sequelae (report AE end date above)				
Unknown				
Fatal				
If fatal, was this event the primary cause of death?	 Yes  No			
If subject died, record date of death:				
Was an autopsy performed?	 Yes	 No	 Unknown	
Was therapy for the event administered?	 Yes  No			
If yes, specify therapy in Description of Event section.				
Was a dechallenge performed?	 Yes  No  NA	 Yes  No  NA	 Yes  No  NA	 Yes  No  NA
If yes, did the event disappear or significantly decrease in intensity after the BI product was stopped?	 Yes  No			
Was the administration correct?	 Yes  No
If the administration was not correct, check all applicable boxes: overdose, abuse, misuse, medication error, other (i.e. occupational exposure, lack of effect, unexpected benefit)	 Misuse / Abuse
	 Medication error
	 Overdose
	 Other:
Action taken with BI studied medication or BI product administered for the disease in scope of ONIS as a result of the event (check one)	Dose not changed 
	Dose reduced 
	Dose Increased 
	Drug withdrawn 
	Not applicable 

 Boehringer Ingelheim	Observational and Non- Interventional Study (ONIS) Adverse Event Form	BI Study No:	Country:
		Site No:	Subject No:

RELEVANT PAST AND CONCOMITANT MEDICATIONS

Please preferably provide trade name. Do not include medications used solely to treat the adverse event(s).

 None  Yes (specify below)	Indication	Past	Start/end dates ddmmmyyyy or cont.	Total daily dose at onset of event (dose/ unit)	Route	Is there a reasonable causal relationship between the event and the past or concomitant therapy? If Yes, record event number from page 2
			Start: End:			 No  Yes Event #
			Start: End:			 No  Yes Event #
			Start: End:			 No  Yes Event #
			Start: End:			 No  Yes Event #
			Start: End:			 No  Yes Event #
			Start: End:			 No  Yes Event #
			Start: End:			 No  Yes Event #
			Start: End:			 No  Yes Event #

ANNEX 9. PREGNANCY MONITORING FORM FOR STUDIES

 Boehringer Ingelheim	Pregnancy Monitoring Form for Studies	BI Trial No.:
		Subject No.:

No. of pages, including cover
page:

To: Boehringer Ingelheim [or CRO] [Address] [Redacted]	From: [site stamp]	Site No.:
[Fax No.] [Redacted]	Country: [Redacted]	

**Please use
this cover page
for each report**

Date received at:

BI OPU or CRO

Date (dd mon yyyy or date stamp)

 Boehringer Ingelheim	Pregnancy Monitoring Form for Studies Part A	BI Trial No.:
		Subject No.:

▶ This form is to be completed by the investigator for reporting any drug exposure during pregnancy after exposure to study medication. The form must be signed, dated and forwarded immediately to the sponsor/CRO (preferably by fax).
 ▶ If in addition a Serious Adverse Event or Adverse Event of Special Interest is experienced, an SAE form must also be completed.

Pregnancy occurred in	 Female study subject  Female partner of a male study subject
-----------------------	--

Demographic Information:

Year of Birth (yyyy):	Height (cm):	Weight (kg):
_____	_____	_____

* Please leave blank, if regulations within your country prohibit the collection of this information.

Medications: Please list all treatments given during pregnancy to date, if available. Continue on a separate sheet if necessary.

Drug name	Route	Daily Dose	Indication for Use	Start Date (dd mmm yyyy)	End Date (dd mmm yyyy)
Trial Drug(s) 1.					
2.					
3.					
Concomitant Medication(s) 4.					
5.					
6.					
7.					

Relevant Maternal History: Any maternal health problems, underlying diseases and medications, smoking, drug and/or alcohol use during the pregnancy, previous infertility therapy, obstetric history including previous miscarriages and pertinent family history:

First day of last menstrual period:	Date (dd mmm yyyy): _____
Estimated date of delivery:	Date (dd mmm yyyy): _____
Enter gestation at time of initial exposure (if known):	No. of weeks: _____
	If weeks not known:
	 1 st trimester  2 nd trimester  3 rd trimester

Date (dd mmm yyyy): _____ Investigator's signature: _____

 Boehringer Ingelheim	Pregnancy Monitoring Form for Studies	BI Trial No.:
		Subject No.:

No. of pages, including cover
page:

To: Boehringer Ingelheim [or CRO] [Address] [Redacted]	From: [site stamp]	Site No.:
[Fax No.] [Redacted]	Country: [Redacted]	

**Please use
this cover page
for each report**

Date received at:

BI OPU or CRO

Date (dd mon yyyy or date stamp)

 Boehringer Ingelheim	Pregnancy Monitoring Form for Studies Part B	BI Trial No.:
		Subject No.:

➤ This form is to be completed by the **investigator** after delivery/termination of pregnancy. The form must be signed, dated and forwarded immediately to the **sponsor/CRO** (preferably by fax).
 ➤ If in addition a Serious Adverse Event or Adverse Event of Special Interest is experienced, an SAE form must also be completed.

Pregnancy occurred in	 Female study subject  Female partner of a male study subject
-----------------------	--

Demographic Information:

Year of Birth (yyyy): _____	Height (cm): _____	Weight (kg): _____
-----------------------------	--------------------	--------------------

** Please leave blank, if regulations within your country prohibit the collection of this information.*

Pregnancy Information:

Birth Outcome (tick the appropriate box)

Unknown		
Induced Abortion		Please complete SAE form
Live Birth		
Normal Newborn		
Congenital Malformation/Anomaly		Please complete SAE form
Spontaneous Abortion/Miscarriage		Please complete SAE form
Still Birth		Please complete SAE form

Multiple Pregnancy	no 	yes 	Enter gestational age at birth (weeks): _____
--------------------	-----------------------------	------------------------------	---

**If yes, please complete an additional page / additional pages for each additional newborn*

Year of Birth (yyyy): _____	Birth weight (grams): _____	Birth Height (cm): _____	APGAR Score (1-10): _____	Gender: male  female 
-----------------------------	-----------------------------	--------------------------	---------------------------	--

Date (dd mmm yyyy): _____	Investigator's signature: _____
---------------------------	---------------------------------
